9.5.2 Secondary Outcomes

1. To analyze physiologic synchrony in GSR, first, an average slope of the GSR will be calculated in the patient and provider recordings in moving 5 second windows, offset by 1 second. Next, Pearson correlations with lag zero will be calculated over successive 15 second windows between time-locked patient and provider GSR slope values. Then, a single session index will be calculated from the ratio of the sum of the positive correlations across the entire visit divided by the sum of the absolute value of the negative correlations across the entire visit. To reduce skew, the natural logarithm of the index will be calculated. Thus, an index value of zero reflects equal positive and negative correlations, a value greater than zero reflects more concordance in GSR than not, while a value less than zero reflects less concordance in the dyad (less than 50%)⁸². These index values will be used in GLM analyses with GERD symptom severity and/or correlated with visit type.

We will also perform similar analyses on the HRV data – comparing variation in the beat-to-beat intervals over short segments of time and calculating Pearson correlation coefficients for time-locked patient and provider data for these intervals.

2. We will calculate absolute changes in both GSR and also high frequency HRV within study subjects from the beginning to the end of the study visit. We will assess the Pearson correlation between these changes and reported changes in GERD symptom severity. We will also look at absolute levels of GSR and HRV at the end of the study visit and compare those values with changes in GERD symptom severity in GLM models. As an exploratory analysis, I will test whether changes in GSR and HRV are a function of baseline perceived stress and if that relationship differs between the standard and expanded visit interventions.
3. To analyze study visit videos, 2 minute thin slices of each video at three time points (beginning, middle, and end of study visits) will be analyzed by trained and blinded coders, for the presence of 1) micro-level non-verbal supportive behaviors (e.g., gazes, smiles, nods, gestures – measured as absolute number or

length of time) as well as 2) macro-level impression ratings of the interaction (e.g., engagement, friendliness, relaxed, empathic, reciprocity – measured on a 1-9 scale). The PI will meet weekly with the coders to review findings and resolve areas of disagreement until greater than 70% concordance is achieved between coders using Cronbach's alpha. Each of these variables will be assessed in a GLM examining time, visit type, and time x visit type effects. We will also calculate the Pearson correlation coefficient for each variable relative to improvement in GERD symptoms and construct a GLM examining patient and provider smiling as a predictor of improvement in GERD symptoms. Other models may also be constructed based on the results of the initial video analyses.

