9. STATISTICAL CONSIDERATIONS

9.1 General Design Issues

Design: This is a single-blinded randomized controlled trial in which subjects will be randomized in a 1:1 fashion to receive either an expanded or standard visit with a healthcare provider about their GERD symptoms and then treated with amitriptyline or omeprazole for 8 weeks to determine whether an expanded visit can augment the effects of a medication compared to a standard visit.

Primary hypotheses:

1. Subjects who receive an expanded visit will have a greater improvement in their GERD symptoms after 8 weeks of treatment with amitriptyline or omeprazole compared to subjects who receive a standard visit.

Secondary hypothesis:

1. Patient-provider dyads in expanded visits will have a greater percentage of the total visit time spent in physiologic concordance (measured by either GSR or HRV) compared patient-provider dyads in standard visits.
2. Percentage of visit time with physiologic concordance (in GSR or HRV) will be correlated with GERD symptom improvement.
3. Subjects who experience physiologic changes similar to those elicited by mind-body techniques (i.e., decreased GSR and increased high frequency HRV) over the course of their visit (first several minutes compared to the last several minutes of the visit) will demonstrate greater improvements in GERD symptom severity than subjects who do not.

4. Healthcare providers in expanded visits will demonstrate more patient-centered non-verbal behaviors (e.g., smiles and gazes) and global impression (e.g., engaged, friendly, relaxed) compared to providers in standard visits as rated by blinded reviews of thin slices of video excerpts.
5. Patient and provider smiling at the end of study visits will be significantly associated with GERD symptom improvement 8 weeks later.

Primary outcome:

1. Change in the average daily GERD symptom severity score from baseline to the last week of the study in the expanded vs. standard group. GERD symptom severity is based on the sum of scores assessing the severity of daytime heartburn, nighttime heartburn, and acid reflux each on a 0-4 point scale (none, mild, moderate, severe, very severe; higher scores signify worse symptoms).

Secondary outcomes:

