1. Ratio of the sum of positive correlations over the sum of negative correlations in GSR (or HRV) across patient-provider encounters for standard vs. expanded visit types and for responders vs. non-responders (those with a 50% or greater improvement in their GERD symptom severity).
2. Absolute change in GSR (or high frequency HRV signal) in patient recordings from the beginning of the study visit to the end of the study visit and correlation with subsequent change in GERD symptom severity.
3. Differences in blinded ratings of 2 minute thin slices of study visit videos from the beginning to the end of the study in supportive global impressions (e.g., engagement, relaxed, patient seems pleased/satisfied) and non-verbal behaviors (e.g., smiling) between standard and expanded visit types and correlation with subsequent change in GERD symptom severity.

Validity and reliability of outcome measures:

1. Assessment of physiologic concordance has been described by a number of groups and we will be using similar methodology^{45,82}.
2. GERD symptom severity will be assessed by a daily symptom diary used by a number of other groups in medication trials and in our previous study^{64,83,84}. The average daily GERD symptom severity is based on the daily sum of scores from the first three questions assessing severity of daytime heartburn, nighttime heartburn, and acid reflux averaged over a 7 day period. The change in GERD symptom severity is calculated by subtracting the average daily GERD symptom severity score during the last 7 days of the study from the average daily GERD symptom severity score at study enrollment. The other GERD symptom questionnaires we are using have also been validated^{26,73,74}.
3. Social psychologists have developed and validated a variety of coding schemes to analyze providers' verbal and non-verbal behaviors and to link these behaviors with patient satisfaction, understanding, trust, rapport, empathy, and a variety of related factors^{9,58-63}. We will use a subset of these validated coding

schemes. Thin slices have shown high reliability and validity for behaviors such as gaze, nods, and smiles⁸⁵.

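### Secondary hypotheses 1 and 2 concern the percentage of visit time in concordance, but the only planned measure is a magnitude-weighted log ratio of correlations, which does not measure time.

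*Combined protocol and SAP*

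**What the plan says.** Section 9.1 (General Design Issues) states secondary hypothesis 1 as expanded-visit dyads having a "greater percentage of the total visit time spent in physiologic concordance" than standard-visit dyads. Secondary hypothesis 2 reads "Percentage of visit time with physiologic concordance (in GSR or HRV) will be correlated with GERD symptom improvement". Both are about a share of time.

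The matching secondary outcome, listed in Section 3 and again in Section 9.1, is something else: "Ratio of the sum of positive correlations over the sum of negative correlations in GSR (or HRV) across patient-provider encounters", compared by visit type and by responder status.

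Section 9.5.2 gives the computation for GSR. "Pearson correlations with lag zero will be calculated over successive 15 second windows" on the slope values, and the session index is the "ratio of the sum of the positive correlations across the entire visit divided by the sum of the absolute value of the negative correlations". Then, "To reduce skew, the natural logarithm of the index will be calculated". Two interpretations follow: "an index value of zero reflects equal positive and negative correlations", and "a value less than zero reflects less concordance in the dyad (less than 50" per cent). The denominator of that 50% is not named. These index values are what goes into the models with symptom severity and visit type. HRV is to be handled similarly, with no segment length given.

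Nowhere do the documents define when a window counts as concordant, or plan an analysis of the percentage of visit time. The table in Section 9.5 mentions physiologic concordance but does not define it.

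**The concern.** A percentage of time counts windows: each 15-second window is concordant or not. The planned index weights each window by the size of its correlation, so a few strong windows can outweigh many weak ones. These are different quantities, and the hypotheses name one while the outcome and analysis use the other.

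The unexplained 50% makes it easy to move from one to the other. The only percentage attached to concordance elsewhere in the plan is percentage of visit time, so a reader will naturally take the 50% that way. Two things are at stake. A result on the index could be described as a result about time spent in concordance, which it is not. And because the hypothesis and the outcome disagree, the choice between them could be made after the data are seen.

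**Working it through.** **Inputs from the documents.** One lag-zero Pearson correlation r per 15-second window, and index = ln(S+ / S-), where S+ is the sum of the positive r and S- the sum of the absolute negative r (Section 9.5.2). Pilot visit lengths average 18 minutes (standard) and 42 minutes (expanded) (Section 5.1). Taking successive windows as non-overlapping, these give 18 × 60 / 15 = 72 and 42 × 60 / 15 = 168 windows.

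**Assumptions, not in the documents.** A window is concordant if r > 0. All values of r below are illustrative.

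**Step 1: reproduce the plan's 50%.** The positive share of the summed |r| is S+ / (S+ + S-) = 1 / (1 + exp(-index)). At index 0 this is 1 / (1 + 1) = 50%. Read that way, the figure is exact.

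**Step 2: try the same figure as visit time.** Let P be the share of windows with r > 0, a the mean positive r, and b the mean absolute negative r. Then

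index = ln[ P × a / ((1 - P) × b) ].

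Setting the index to 0 gives P = b / (a + b), which is 50% only if a = b. Nothing in the plan makes a and b equal.

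**Step 3: single-visit examples.**

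- 60% of windows at +0.2 and 40% at -0.5: ln(0.6 × 0.2 / (0.4 × 0.5)) = ln(0.60) = -0.51. The index is below zero with 60% of time concordant.
- 40% at +0.8 and 60% at -0.3: ln(0.4 × 0.8 / (0.6 × 0.3)) = ln(1.78) = +0.58. The index is above zero with 40% of time concordant.

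**Step 4: a contrast between visit types at the pilot lengths.**

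| Visit | Windows with r > 0 | Windows with r < 0 | Share of time | Index |
|---|---|---|---|---|
| Expanded (168) | 101 at +0.2 | 67 at -0.4 | 60.1% | ln(20.2 / 26.8) = -0.283 |
| Standard (72) | 29 at +0.6 | 43 at -0.3 | 40.3% | ln(17.4 / 12.9) = +0.299 |

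By share of time the expanded visit is higher, as hypothesis 1 predicts. By the planned index the standard visit is higher.

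**Step 5: when the signs disagree.** With P above 50%, the index is negative when b / a exceeds P / (1 - P): 1.22 at P = 55%, 1.50 at 60%, 1.86 at 65% and 2.33 at 70%. Equivalently, S+ minus S- is the sum of all r, so the index is positive exactly when the mean r is positive. The share of time exceeds 50% when the median r is positive. Disagreement needs mean and median on opposite sides of zero.

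**Step 6: how often that might happen.** An illustrative simulation used 1 Hz series with AR(1) increments (coefficient 0.5), 5-second slopes, and 72 or 168 windows. None of these settings except the slope and window lengths and the pilot visit durations comes from the documents.

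| Assumed dyad coupling | Correlation of index with share of time | Index sign disagrees with 50% line | Group direction disagrees (30 per group, no built-in difference) |
|---|---|---|---|
| Varies, SD 0.1, mean 0 or 0.1 | 0.95 to 0.97 | 5% to 11% of dyads | 9% of draws |
| None | about 0.85 | 17% to 20% of dyads | 17% of draws |

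**The case against.** The strongest reply is that the outcome, its formula and its use are pre-specified and agree with one another. Sections 3 and 9.1 list the ratio as secondary outcome 1, Section 9.5.2 defines it and carries it into the analyses, and only the wording of two hypotheses differs. That stands. A reader might infer that the index is an unplanned measure, or that concordance goes unanalysed. The documents do not support either inference: the gap is between hypothesis and listed outcome.

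A reader might also infer that the 50% remark is simply wrong. It is not shown to be. As the positive share of summed |r| it is exact, and the preceding remark, that zero means positive and negative correlations are equal, fits that reading. It is false only if taken as visit time. The fair criticism is that its denominator is missing, and that hypotheses 1 and 2 steer the reader to the wrong one.

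Finally, the reversals in steps 3 and 4 rest on constructed values in which the more frequent sign is much the weaker. This also stands: reversal is possible but not typical. In the simulation the measures agreed closely when coupling varied, and disagreed most when there was no coupling to report. None of this removes the mismatch, because close agreement in most dyads does not make a magnitude-weighted ratio a percentage of time.

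**Conclusion.** The point holds as a mismatch between hypothesis and measure. Followed as written, the plan tests the relative strength of positive and negative correlation, and does not test secondary hypotheses 1 and 2 as worded. Index zero marks 50% of summed |r|, and marks 50% of visit time only when a = b.

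The algebra needs only the plan's own formula and the convention that concordant means r > 0. The size of any practical discrepancy depends on the distribution of r, which the documents do not give. Under the assumed conditions above, the index sign and the 50% line disagreed in 5% to 20% of dyads, and the two measures usually agreed.

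Two stronger readings should be resisted. A reader might infer that this is the trial's main mechanism result, but Section 9.1 lists five secondary hypotheses without ranking them. A reader might also infer that the result will be misreported, but the documents do not say how it will be described, so this is a risk to close off and not a prediction. The primary outcome, its ANCOVA and the sample size are unaffected. The correction should be made because it is specific and nearly free.

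**What to change.** 1. In Section 9.1, restate hypotheses 1 and 2 in terms of the log index, that is, the relative strength of positive and negative correlation over the visit. The index stays the listed secondary outcome.
2. In Section 9.5.2, delete the 50% remark or define it as the positive share of summed |r|.
3. From the same windows, compute the proportion with r > 0. Report it by visit type and against symptom improvement, as supportive, and make it the only result described as percentage of visit time.
4. State the HRV segment length and apply the same definitions to HRV.

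The cost is a wording change and one extra summary from correlations already planned, with no new data. The downside is one more supportive secondary result, correlated with the index. If the investigators would rather keep the hypotheses in terms of time, the proportion of windows would have to become the measure that tests them, with the index supportive. Either is coherent if fixed before the data are analysed. The first needs no change to the listed outcome.

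### The end-of-visit GSR and HRV models name no start-of-visit covariate, so they mix a person's habitual level with the within-visit response that hypothesis 3 concerns

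*Combined protocol and SAP*

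**What the plan says.** Secondary hypothesis 3 in Section 9.1 predicts that subjects whose physiology moves towards relaxation over the visit, with "decreased GSR and increased high frequency HRV", will improve more. The matching outcome, in Sections 3 and 9.1, is "Absolute change in GSR (or high frequency HRV signal) in patient recordings from the beginning of the study visit" to its end, correlated with later symptom change.

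Section 9.5.2 item 2 sets out two analyses:

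- **Change score.** "We will calculate absolute changes in both GSR and also high frequency HRV within study subjects", taken over the course of the visit, and then: "We will assess the Pearson correlation between these changes and reported changes in GERD symptom severity".
- **End level.** "We will also look at absolute levels of GSR and HRV at the end of the study visit", with those values related to symptom change in GLMs. This sentence says HRV without repeating the high-frequency qualifier.

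No covariates are listed for the end-level GLMs. The table in Section 9.5 gives Current Stress as a covariate for GLM analyses in general. Start-of-visit GSR or HRV is not named as a covariate anywhere. The plan does use a baseline covariate for the primary outcome (Section 9.5.1), and it uses a log for the synchrony index in item 1: "To reduce skew, the natural logarithm of the index will be calculated". Item 2 states neither.

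**The concern.** The end-of-visit value of a physiologic marker has two parts: the level the person brought into the room and what happened during the visit. Only the second part bears on hypothesis 3. If people differ in habitual level by as much as, or more than, they move within a visit, an unadjusted end level is mostly a measure of who the person is.

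Two errors follow. A real within-visit effect is diluted and may be missed. And if habitual autonomic level happens to be related to symptom change, the analysis can return a significant result that reads as a response to the visit when nothing happened in the visit. The second is the more serious, because identifying physiologic markers is a stated secondary aim and such a result would be taken as support for the mechanism.

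**Working it through.** **The plan's own figure.** The only sample-size figure is the table of minimal detectable differences in Section 9.2, for the primary outcome. With 30 per group, 80% power and two-sided alpha 0.05, the two-sample t calculation (58 df) gives 1.103, 1.471 and 1.839 at SD 1.5, 2.0 and 2.5. This agrees with the stated 1.10, 1.47 and 1.84. No figure is given for secondary outcome 2. For scale, the smallest correlation detectable with 80% power at n = 60 is tanh(2.802/√57) = tanh(0.371) = 0.355, so there is little room for dilution.

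**Inputs.** From the documents: n = 60 and two-sided alpha 0.05. Assumed: a true correlation of 0.35 between within-visit change and symptom change, and all marker variances. The documents give no mean, SD or skew for GSR or HRV, so ranges are shown.

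**Additive model, lost power.** Let S be the start level, W the within-visit change (uncorrelated with S), E = S + W the end level, and k = SD(S)/SD(W). If symptom change correlates 0.35 with W and not with S, then corr(E, symptoms) = 0.35/√(1 + k²). Power is approximately Φ(atanh(r)·√57 − 1.96), with √57 = 7.550. For the change score itself, atanh(0.35) × 7.550 = 2.759, and power is Φ(0.80) = 0.79.

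**Additive model, false attribution.** Now let symptom change correlate 0.35 with S and not at all with W. Then corr(E, symptoms) = 0.35k/√(1 + k²), and any significant result is a trait read as a visit response.

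| k | r, real visit effect | power, end level unadjusted | r, trait only | significant, end level unadjusted |
|---|---|---|---|---|
| 1 | 0.247 | 0.48 | 0.247 | 0.48 |
| 2 | 0.157 | 0.22 | 0.313 | 0.69 |
| 3 | 0.111 | 0.13 | 0.332 | 0.74 |

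Simulation (6,000 trials of n = 60) agrees: 0.49, 0.22 and 0.13 for power, and 48% to 75% for false attribution. With the start level in the model, power is 0.79 to 0.80 and false attribution about 5%.

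**Proportional model.** Here end = start × exp(change), with log-normal start levels. With a between-person log SD of 0.6 to 1.2 and a log-change SD of 0.4 to 0.6, the unadjusted raw end level has power 0.10 to 0.38. The log end level adjusted for the log start level has 0.78 to 0.80. In the trait-only case the unadjusted end level is significant in 38% to 55% of trials.

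**Wider range.** Including milder between-person spread and both models, unadjusted power runs from about 0.06 to 0.64. Unadjusted false attribution starts at about 15%, against 4% to 7% once adjusted. The dilution is mild only where people differ little in level relative to how far they move.

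**Does the scale matter?** For the covariate adjustment, it matters how much is recovered. In one proportional setting (assumed true r 0.40, log SDs 1.0 and 0.3, mean log shift −0.2), the raw end level alone correlates 0.087 with symptoms, adjusted for the raw start level 0.237, raw change 0.218, and log change 0.401. Adjustment on the raw scale brings the end level up to about the raw change score; the rest depends on a scale that suits the marker.

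For the change score, which scale is better depends on how change behaves (true r 0.35 again):

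| If within-visit change is | power, raw change | power, log change |
|---|---|---|
| proportional to level | 0.36–0.76 | about 0.79 |
| additive, unrelated to level | 0.78–0.80 | 0.46–0.77 |

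**The case against.** Three points can be made for the plan, and most of each stands.

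First, hypothesis 3 is about change, and the change analysis comes first in item 2. The end-level models are an addition and do not replace that test. This limits the damage but does not make the additional analysis interpretable.

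Second, silence is not exclusion. The covariates of the end-level GLMs are not listed, and Section 9.5 includes ANCOVA among the general linear models to be used. A reader might infer that the plan rules out start-of-visit adjustment; the text does not say so. It does leave the choice open until the data are seen.

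Third, a reader might infer that the absolute change score has the same defect, and that both markers must be analysed on the log scale with raw change reduced to description. The documents do not support this. A within-subject difference already subtracts the person's own start level, and in an additive model it loses nothing. It depends on level only if change scales with level, and no GSR or HRV distribution is given that would show this for either marker. A simulation that generates proportional change will favour the log; one that generates additive change reverses the ranking, as the last table shows. Logging the synchrony index in item 1 says nothing about the scale of these two markers.

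**Conclusion.** The point holds for the end-of-visit analysis. As written, it does not separate habitual level from within-visit response, under either additive or proportional change. At n = 60 and an assumed correlation of 0.35 it loses most of its power in most settings examined, and it can present a trait as a visit effect in roughly 15% to 75% of trials where only the trait matters. Start-level adjustment returns that rate to about 5% and brings power to about that of the change score on the same scale.

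These sizes rest on assumed correlations and variances, and on treating the start-of-visit recording as an error-free measure of habitual level. A noisy start window would leave some trait effect after adjustment. The direction of the problem does not depend on those values.

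The conclusion does not extend to a claim that between-person differences overwhelm the raw change score, or that the log scale is required. The matter concerns one secondary outcome; the primary ANCOVA and the sample size are untouched.

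**What to change.** In Section 9.5.2 item 2, add a sentence such as: *Each GLM of an end-of-visit marker will include the same subject's start-of-visit value of that marker, on the same scale, as a covariate.* State also that the HRV measure is the high-frequency one, if that is what is meant.

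Keep the absolute change score as planned. Pre-specify ln(end) − ln(start) as a sensitivity analysis for each marker. Alternatively, choose the scale for each marker from its own distribution, blind to symptom outcome, and record the choice before the analysis.

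The cost is two or three sentences, one degree of freedom per model and no new data, since the start value is already needed for the change score. Once adjusted, the end-level model and the change score ask nearly the same question, so agreement between them should not be reported as independent confirmation.
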